4.6. Good Clinical Practice Statement

This study will be conducted according to all stipulations of the protocol, including all statements regarding confidentiality, and in compliance with International Conference of Harmonisation (ICH) guidelines, and all applicable US federal regulations and local legal and regulatory requirements.

4.7. Population to Be Studied

Study subjects will be male or female, 18 years of age and older, with a patient-reported history of KCS for a period of at least 6 months and a clinical diagnosis of bilateral KCS supported by OTX-101-2016-001 study assessments.

5. STUDY OBJECTIVES

5.1. Primary Objective

The primary objective of this study is to evaluate the long-term safety of OTX-101 0.09% in subjects with KCS.

6. INVESTIGATIONAL PLAN

6.1. Overall Study Design

This will be an extension of OTX-101-2016-001, a randomized, multicenter, double-masked, vehicle-controlled study that enrolled male and female subjects, 18 years of age and older, with a patient-reported history of KCS for a period of at least 6 months, a clinical diagnosis of bilateral KCS supported by OTX-101-2016-001 study assessments, and corrected Snellen VA of better than 20/200 in both eyes at Screening and at Baseline.

Subjects who complete Visit 5 (Day 84) of Study OTX-101-2016-001 may be eligible to enroll in protocol OTX-101-2016-002 within 14 days at the discretion of the Principal Investigator and Sponsor. Subjects who provide written informed consent at Visit 5a and meet the inclusion/exclusion criteria requirements will be enrolled in the study and receive study medication (OTX-101 0.09%). All subjects will participate for at least 40 weeks. Subjects who were randomized to the vehicle arm in Study OTX-101-2016-001 may have the opportunity to participate for additional 12 weeks, total of 52 weeks.

Subjects will self-administer study medication topically to both eyes BID from Visit 5a to Visit 8 (Day 364) or Visit 9 (Day 448). Safety evaluations will be conducted at all study visits. The window for Visits 6 and 7 will be ± 7 days. The window for Visit 8 will be +14 days for those subjects assigned to OTX-101 0.09% in Study OTX-101-2016-001 (± 14 days for subjects assigned to vehicle in Study OTX-101-2016-001, participating for 52 weeks in Study OTX-101-2016-002), and Visit 9 will be +14 days. Both eyes will be assessed at each visit. Adverse events and concomitant medications will be documented from signing of informed consent at each study visit.

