
Methodology: This is an open-label extension of OTX-101-2016-001, a randomized, multicenter, double-masked, vehicle-controlled study in which subjects were randomized to 1 of 2 treatment arms and treated for 12 weeks as follows:
 
 • OTX-101 0.09% (N = ■■■ subjects) • Vehicle (N = ■■■ subjects) 
Subjects successfully completing Study OTX-101-2016-001 may be eligible to enroll in this 40 to 52 week open label extension study in which all subjects will receive OTX-101 0.09% therapy. Subjects may also use unpreserved artificial tears, as needed. Subjects assigned to OTX-101 0.09% in Study OTX-101-2016-001 will participate for 40 weeks. Subjects assigned to vehicle in Study OTX-101-2016-001 are eligible to participate for 52 weeks. Both subject sets will total 52 weeks of participation receiving OTX-101 0.09%.
 
Subjects may enroll in Study OTX-101-2016-002 for up to 14 days following completion of Visit 5 of Study OTX-101-2016-001. At Visit 5a, sites will obtain signed informed consent and dispense study medication. If Visit 5a is not conducted on the same day as Visit 5 of Study OTX-101-2016-001, any female subject of childbearing potential must also have a negative urine pregnancy test. Study “Day” approximately reflects the cumulative number of days of exposure to study drug since the baseline visit of Protocol OTX-101-2016-001, regardless of actual calendar time elapsed.
 
Subjects will self-administer study medication topically to both eyes BID for 40 to 52 weeks depending on their treatment assignment in Study OTX-101-2016-001. Safety evaluations for all subjects will be conducted at study visits on Days 182, 273 and 364; the window for Visits 6 (Day 182) and Visit 7 (Day 273) will be ± 7 days; the window for Visit 8 (Day 364) will be +14 days for those subjects assigned to OTX-101 0.09% in Study OTX-101-2016-001. (± 14 days for subjects assigned to vehicle in Study OTX-101-2016-001, participating for 52 weeks in Study OTX-101-2016-002). Subjects assigned to vehicle in Study OTX-101-2016-001, participating for 52 weeks in Study OTX-101-2016-002, will also be evaluated at Visit 9 (Day 448), which will have a visit window of +14 days. Both eyes will be assessed at each visit. Adverse events and concomitant medications will be documented from signing of informed consent to the subject’s final visit.
	

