Exclusion Criteria (continued):

12. Presence of conjunctivochalasis (i.e., mechanical blockage of the lower lid punctum by redundant conjunctiva).
13. Presence of pterygium in either eye.
14. Unwilling to discontinue use of contact lenses during the duration of the study.
15. Preplanned elective surgery or hospitalization during the study period.
16. HIV-positive.
17. Unable to reliably report symptoms and history.
18. Has a severe/serious ocular condition, or any other unstable medical condition that, in the Investigator's opinion, may preclude study treatment or follow-up.
19. Women who are pregnant or breastfeeding.

Investigational Product, Dosage, and Mode of Administration: OTX-101 0.09%, 1 drop in both eyes BID

Reference Therapy, Dosage, and Mode of Administration: N/A

Duration of Treatment: 40 - 52 weeks

Study Procedures: Ophthalmic examinations must be conducted in the order listed in the Schedule of Procedures.

Visit 5a

The site will obtain signed informed consent, inclusion/exclusion criteria, and dispense study medication. If Visit 5a is not conducted on the same day as Visit 5 of Protocol OTX-101-2016-001, the site will also update concomitant medications and conduct a urine pregnancy test for female subjects of childbearing potential.

Visits 6 and 7 (Days 182 and 273)

The site will update concomitant medications, conduct a urine pregnancy test for female subjects of childbearing potential, conduct ophthalmic examinations as specified, document any AEs, and dispense study medication.

Visit 8 (Day 364): Final Treatment Visit for Subjects assigned to OTX-101 0.09% in Study OTX-101-2016-001

The site will update concomitant medications, conduct a urine pregnancy test for female subjects of childbearing potential, conduct ophthalmic examinations as specified and document any AEs. Study medication will be dispensed to those subjects continuing in the study for an additional 12 weeks.

Visit 9 (Day 448): Final Treatment Visit for Subjects assigned to vehicle in Study OTX-101-2016-001

The site will update concomitant medications, conduct a urine pregnancy test for female subjects of childbearing potential, conduct ophthalmic examinations as specified and document any AEs.

Clinical site personnel will document all received and returned study medication at each visit. Study medication accountability will be conducted by the monitor at each applicable monitoring visit.

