7.3. Subject Withdrawal Criteria

The following are the criteria for considering withdrawal from the study:

- Withdrawal of patient consent.
- Subject lost to follow-up.
- The subject has a clinically significant adverse event (AE) or serious adverse event (SAE) that would not be consistent with continuation in the study, as determined by the Investigator in discussion with the Medical Monitor.
- Pregnancy.

If a subject withdraws or is withdrawn from the study, the principal reason for withdrawal will be recorded on the electronic case report form (eCRF). If a study subject is discontinued from study medication before the final scheduled visit, all procedures scheduled for that visit should be conducted at the time the subject is discontinued.

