### **2.2. Study Design**

This will be an extension of OTX-101-2016-001, a randomized, multicenter, double-masked, vehicle-controlled study that enrolled male and female subjects, 18 years of age and older, with a patient-reported history of KCS for a period of at least 6 months, a clinical diagnosis of bilateral KCS supported by OTX-101-2016-001 study assessments, and corrected Snellen visual acuity (VA) of better than 20/200 in both eyes at Screening and at Baseline.

Subjects who complete Visit 5 (Day 84) of Study OTX-101-2016-001 may be eligible to enroll in protocol OTX-101-2016-002 within 14 days at the discretion of the Principal Investigator and Sponsor. Subjects who provide written informed consent at Visit 5a and meet the inclusion/exclusion criteria requirements will be enrolled in the study and receive study medication (OTX-101 0.09%). All subjects will participate for at least 40 weeks. Subjects who were randomized to the vehicle arm in Study OTX-101-2016-001 may have the opportunity to participate for an additional 12 weeks, and a total of 52 weeks.

Subjects will self-administer study medication topically to both eyes twice daily (BID) from Visit 5a to Visit 8 (Day 364) or Visit 9 (Day 448). Safety evaluations will be conducted at all study visits. The window for Visits 6 and 7 will be  $\pm 7$  days. The window for Visit 8 will be +14 days for those subjects assigned to OTX-101 0.09% in Study OTX-101-2016-001 ( $\pm 14$  days for subjects assigned to vehicle in Study OTX-101-2016-001, participating for 52 weeks in Study OTX-101-2016-002), and for Visit 9 the window will be +14 days. Both eyes will be assessed at each visit. Adverse events (AEs) and concomitant medications will be documented at each study visit from signing of informed consent to Day 364.

A total of approximately 700 subjects will be enrolled in Protocol OTX-101-2016-001 (approximately 350 subjects in each treatment arm) at approximately 50 clinical sites. Subjects who successfully complete that study may be eligible to participate at the discretion of the Principal Investigator and the Sponsor with the goal of enrolling approximately 300 subjects in Protocol OTX-101-2016-002.

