### **7.1. Subject Disposition**

Subject disposition, including the number of subjects entering the extension phase and completing the extension phase will be tabulated. The percentage of subjects treated and completing the study will be based on the total number entering the extension phase. A subject data listing will be provided.

The total number and percentage of subjects included in each of the analysis datasets will be summarized with percentages based on the total number of subjects entering the extension phase. A subject data listing will be provided.

Discontinuations and the reasons for discontinuation from the study will be summarized for all subjects. Summaries will include the number and percentage of subjects. Reasons for discontinuation following the receipt of study drug will include the following:

- Withdrawal by Subject
- Lost to Follow-up
- Adverse Event
- Pregnancy
- Death
- Physician Decision
- Protocol Deviation
- Other

A subject data listing will be provided.

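### The documents disagree on whether a vehicle-origin subject who stops at Visit 8 (40 weeks) has completed the study, so the stop can be tabulated as completion with no reason recorded

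*Protocol*

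**What the plan says.** Vehicle-origin subjects here are those randomised to vehicle in the parent study, OTX-101-2016-001. The documents describe their last 12 weeks in two ways.

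**As optional.** Protocol 6.1 states "All subjects will participate for at least 40 weeks" and then "Subjects who were randomized to the vehicle arm in Study OTX-101-2016-001 may have the opportunity to participate for additional 12 weeks". SAP 2.2 says these subjects "may have the opportunity to participate for an additional 12 weeks, and a total of 52 weeks". For Visit 8 the synopsis says "Study medication will be dispensed to those subjects continuing in the study for an additional 12 weeks". Notes h and i of the Schedule of Procedures likewise make dispensing, and the wider Visit 8 window, conditional on taking part in the extra 12 weeks. SAP 5.1 describes the cohort as having nine months of active exposure or more, not twelve.

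**As part of the planned course.** The synopsis (Methodology) states "Both subject sets will total 52 weeks of participation receiving OTX-101 0.09"%. Its visit descriptions name Visit 9 (Day 448) as the final treatment visit for the vehicle arm, and Protocol 10.3 makes the final visit depend on parent-study assignment. One synopsis sentence sits between the two: "Subjects assigned to vehicle in Study OTX-101-2016-001 are eligible to participate for 52 weeks".

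**On recording and tabulation.** Protocol 7.3 says "If a subject withdraws or is withdrawn from the study, the principal reason for withdrawal will be recorded on the electronic case report form". SAP 7.1 says that disposition, "including the number of subjects entering the extension phase and completing the extension phase will be tabulated". It defines completion for neither arm, and none of its eight discontinuation reasons is for not taking up the extra 12 weeks. SAP 8 lists no changes from the protocol, so the SAP does not settle the matter.

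**The concern.** Long-term safety is the only objective, and the vehicle-origin cohort receives OTX-101 for the first time in this study. If a site treats Visit 8 as a legitimate end for these subjects, someone who has had enough of the drops can leave there without being a withdrawal. Nothing then obliges the site to ask why. With about 50 sites and two available readings, similar subjects could also be classified differently.

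Two things are at stake. First, the completion figure for this arm may mix 40-week and 52-week completers, and some stops for poor tolerability may be missing from the discontinuation counts. Second, no missing data are imputed (SAP 6), and visual acuity and IOP are summarised by visit (SAP 7.7 and 7.8). Visit 9 results therefore describe only those who stayed, and the reader would not know why the others left. The same selection applies to any vehicle-origin subjects in the One Year Safety Population of Protocol 11.5.1.1, who can reach a year on drug only by staying. A reason that was not collected cannot be supplied later by the analysts.

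**Working it through.** **1. Timing (Schedule of Procedures).** Visit 5a is Day 84.
- Visit 8: 364 − 84 = 280 days, and 280 / 7 = 40 weeks. This reproduces the 280 days in the schedule.
- Visit 9: 448 − 84 = 364 days, and 364 / 7 = 52 weeks.
- For continuing vehicle-origin subjects the Visit 8 window is ±14 days: 280 − 14 = 266 to 280 + 14 = 294 days.

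A stop at Visit 8 is thus 12 weeks short of the 52 weeks that the synopsis states for both sets.

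**2. Classification of a stop at Visit 8.**
- Under Protocol 6.1, SAP 2.2 and SAP 5.1, the subject has met the 40-week minimum and has not taken up an opportunity. Protocol 7.3 is not clearly triggered, so no reason is required.
- Under the synopsis and Protocol 10.3, the subject has stopped before the scheduled final visit. Protocol 7.3 is triggered and a reason is recorded.
- The synopsis instruction on early discontinuation refers to stopping before Visit 8 or Visit 9, whichever applies. It does not say which one applies to a vehicle-origin subject who does not continue.

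**3. What the planned outputs would show.**
- *Exposure (SAP 7.5, Table 14.3.8).* Three months is given as 90 days and twelve as 360, so nine months is taken as 270. Counting from the first OTX-101 dose, a stop at 280 days falls in the 9-to-under-12-month row. A stop at 266 days falls one row lower. Completion of Visit 9 at 364 days falls in the top row. The shorter duration is visible; the reason is not. A subject stopping for an adverse event at day 300 shares the row with a subject who ended at Visit 8.
- *Visit participation (Table 14.1.3).* This table should show Visit 8 attended and Visit 9 not, again without a reason.
- *Adverse events (Protocol 9.7, SAP 7.6, Table 14.3.1.5).* An event whose recorded action is permanent discontinuation of study drug is tabulated whatever the disposition status.
- *Disposition (SAP 7.1, Table 14.1.2).* Presentation by parent arm under SAP 5.1 does not separate 40-week from 52-week completers within the vehicle-origin arm.

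**4. Possible size (illustration only).** Unrecorded tolerability stops = N × share not continuing × share of those for tolerability. The documents give neither share. Assumed ranges are 5% to 30% and 10% to 50%. For N, an even split of the 258 enrolled (SAP 9) is assumed, giving 258 / 2 = 129; the planned figures (SAP 4) give up to about 300 − 150 = 150.

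| Shares assumed | N = 129 | N = 150 | Share of cohort |
|---|---|---|---|
| 5% × 10% | 0.6 | 0.8 | 0.5% |
| 10% × 25% | 3.2 | 3.8 | 2.5% |
| 30% × 50% | 19.4 | 22.5 | 15% |

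For any chosen pair of shares the result is an upper bound, because stops coded as due to an adverse event would still be counted in SAP 7.6.

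**The case against.** The strongest reply is that the protocol already answers the question. The synopsis names Visit 9 as the vehicle arm's final visit, section 10.3 makes the final visit depend on assignment and not on preference, and sections 8.2, 8.5.1 and 8.5.2.3 speak of subjects scheduled to go on to Visit 9. On that reading a Visit 8 stop is a withdrawal with a reason, and SAP 7.1 already offers an adverse-event category and a subject-withdrawal category. Even if disposition fails, adverse events are sought at every visit, each carries an action code, and the SAP tabulates those leading to permanent discontinuation. The exposure and visit-participation tables and the listings show who stopped near 40 weeks.

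Much of this stands. A reader might infer that the plan counts Visit 8 stops as completion, that discontinuations for adverse events are therefore understated, or that the selection is invisible. The documents support none of these. No passage assigns such stops to completion, adverse-event stops have their own route into the tables, and the shorter duration can be seen.

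The reply does not remove the conflict, because Protocol 6.1 and both SAP sections allow a 40-week end for this arm. The adverse-event route also works only if the investigator codes the event as leading to discontinuation. A site that regards Visit 8 as a proper end need not do so for a mild event. In Phase 2b (Protocol 4.4), instillation site pain was reported by 15.1% at 0.09%, and ocular events were predominantly mild to moderate and needed no action on study drug. That makes uncoded reluctance plausible; it does not show that it occurred.

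**Conclusion.** The point holds as an unresolved conflict with a practical consequence: the status of a vehicle-origin subject who stops at Visit 8 is undefined, and such a stop can be tabulated as completion without a reason unless an adverse event is coded as leading to permanent discontinuation. It should be corrected, because the lost information cannot be recovered at analysis.

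No number affected can be derived from the documents. The illustration, from about 1 to about 23 subjects, rests wholly on the assumed shares and cohort size and should not be quoted as an estimate.

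The reach is limited to disposition and tolerability-discontinuation rates, and to the interpretation of Visit 9 data, in the vehicle-origin cohort. The analysis is descriptive, so no hypothesis test is affected. The 100-subject one-year recommendation is planned around at least 150 OTX-101-origin subjects (SAP 4), for whom Visit 8 is the final visit on every reading, so that cohort is untouched.

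**What to change.** 1. Reconcile the protocol synopsis and section 10.3 with Protocol 6.1, schedule notes h and i, SAP 2.2 and SAP 5.1, so that all give the same status to a vehicle-origin subject who does not go on after Visit 8.
2. In Protocol 7.3 and the Visit 8 procedures (10.2.1 and 10.3), record for each vehicle-origin subject whether he or she continues and, if not, the main reason, using the SAP 7.1 list.
3. In SAP 7.1, define completion separately by parent-study arm. In Table 14.1.2, show for the vehicle-origin cohort: completed Visit 8, continued, did not continue by reason, and completed Visit 9. Count non-continuation driven by an adverse event among discontinuations due to adverse event.
4. If the new item comes too late for some subjects, keep the definition and the rows and show their reason as not recorded.

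The cost is one eCRF item and a few table rows. Discontinuation figures may look slightly less favourable.

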6.2. Number of Subjects

A total of approximately [REDACTED] subjects will be enrolled in Protocol OTX-101-2016-001 (approximately [REDACTED] [REDACTED] at approximately 50 clinical sites. Subjects who successfully complete that study may be eligible to participate at the discretion of the Principal Investigator and the Sponsor with the goal of enrolling approximately [REDACTED] subjects in Protocol OTX-101-2016-002.

6.3. Treatment Assignment

The treatment assignments will be:

- OTX-101 0.09%

6.4. Criteria for Study Termination

The study may be terminated at any time by the Sponsor following appropriate notification.

7. SELECTION AND WITHDRAWAL OF SUBJECTS

7.1. Subject Inclusion Criteria

The subject will be included if he/she meets the following inclusion criteria:

1. Successful completion of participation in Protocol OTX-101-2016-001.
2. All subjects must provide signed written consent prior to participation in any study related procedures.
3. Female subjects of childbearing potential must have a negative urine pregnancy test at Visit 5 (Day 84) of Protocol OTX-101-2016-001 or at Visit 5a of Protocol OTX-101-2016-002, if conducted at a later date. Women of childbearing potential (i.e., women who are not either postmenopausal for one year or surgically sterile) and men who have partners of childbearing potential must use an acceptable form of contraception throughout the study.
4. Corrected Snellen visual acuity (VA) of better than 20/200 in both eyes at Visit 5 (Day 84) of Protocol OTX-101-2016-001.

7.2. Subject Exclusion Criteria

The subject will be included in the study if they meet the inclusion criteria listed in Section 7.1 and do not meet the exclusion criteria listed below.

1. Subjects reporting an Adverse Event that has not resolved by Visit 5 of Protocol OTX-101-2016-001 may be excluded if, in the judgment of the Principal Investigator and Medical Monitor, it would not be in the subject's best interest to continue treatment with study drug.
2. Use of Restasis or any topical cyclosporine preparation following Visit 5 of Protocol OTX-101-2016-001.
3. Use of any prescription topical ophthalmic medications (including antiglaucoma medications) other than the assigned study medication during the study period. Unpreserved artificial tears are permitted.
4. Current active eye disease other than KCS (i.e., any disease for which topical or systemic ophthalmic medication is necessary).
5. History of herpes keratitis.
6. Unstable macular disease (e.g., age-related macular degeneration, diabetic maculopathy). Stable macular disease is defined as no reduction in central VA since the screening visit of Study OTX-101-2016-001.
7. Diagnosis of chronic uveitis.
8. Corneal transplant following Visit 5 of Study OTX-101-2016-001.

9. Corneal refractive surgery following Visit 5 of Study OTX-101-2016-001.
10. Non-laser glaucoma surgery following Visit 5 of Study OTX-101-2016-001.
11. Lagophthalmos or clinically significant eyelid margin irregularity of the study eye whether congenital or acquired.
12. Presence of conjunctivochalasis (i.e., mechanical blockage of the lower lid punctum by redundant conjunctiva).
13. Presence of pterygium in either eye.
14. Unwilling to discontinue use of contact lenses during the duration of the study.
15. Preplanned elective surgery or hospitalization during the study period.
16. HIV-positive.
17. Unable to reliably report symptoms and history.
18. Has a severe/serious ocular condition, or any other unstable medical condition that, in the Investigator's opinion, may preclude study treatment or follow-up.
19. Women who are pregnant or breastfeeding.

